### **5.7 Study Discontinuation:**

The NIH, RDCRN DSMB and local IRBs (at their local site) have the authority to stop or suspend this trial at any time. This study may be suspended or closed if:

- Early stopping rules have been met. The early stopping rule will be that the study will end if any apparent toxic effect of the medications occurs. These toxic effects include allergic manifestations, including rash, and including nausea, vomiting, or other symptoms that lead a patient to not tolerate the medication.
- Accrual has been met.
- The study objectives have been met.
- The Study Chair / Study Investigators believe it is not safe for the study to continue.
- The RDCRN DSMB suspends or closes the trial.
- The NIH suspends or closes the trial.

### **5.8 Subject Discontinuation:**

An intent to treat approach will be used. All data acquired prior to termination for the reasons outlined below will be included in the primary analysis unless patient withdraws consent. Every effort will be made to conduct a final study visit with the participant and participants will be followed clinically until, if applicable, all adverse events resolve.

- Withdrawal of consent
- Withdrawal by the participant
- Withdrawal by the investigator
- Intercurrent illness or event that precludes further visits to the study site or ability to evaluate disease (e.g.-mental status change, large pleural effusion).

## **5.9 Data Quality and Monitoring Measures:**

As much as possible data quality is assessed at the data entry point using intelligent on-line data entry via visual basic designed screen forms. Data element constraints, whether independent range and/or format limitations or ‘relative’ referential integrity limitations, can be enforced by all methods employed for data input. QA reports assess data quality post-data entry. As we note, data quality begins with the design of the data collection forms and procedures and incorporates reasonable checks to minimize transcription and omission errors. Of the more important quality assurance measures are the internal validity checks for reasonableness and consistency.

## **6 Statistical Considerations**

The impact of CBTD dose on CysCap will be analyzed with a mixed effects model, with subject as a repeated factor, and including dose and period effects.

### **6421 Sample Size**

The primary endpoint is defined as a mean change in Cystine Capacity (CysCap). In a previous study, we saw the highest change in CysCap between dose 0mg/d vs. dose 1mg/d. With this large effect size, we would need 9 participants ( $P=0.05$ , power 85%) in this protocol. We plan to enroll 15 participants in this protocol. This should account for potential patient withdrawal or other unforeseen protocol issues.

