# Effect of Increasing Doses of Tiopronin on Cystine Capacity in Patients with Cystinuria

## 1. Synopsis

Protocol Number:	6421
Protocol Title:	Effect of Increasing Doses of Tiopronin on Cystine Capacity in Patients with Cystinuria
Study Chair:	[name]
Statistician:	[name]
Consortium:	Rare Kidney Stone Consortium
Participating Sites:	New York University Langone Health, New York, NY
Activation Date:	09/10/2018
Sample Size:	15 subjects
Target Enrollment Period:	1 year
Study Design:	Crossover trial of escalating doses
Primary Study Objective:	To evaluate the effect of escalating doses of cystine binding thiol drugs on the cystine capacity of the urine. The overall goal will be to help guide therapy and ultimately minimize unnecessary side effects caused by larger dosages.
Secondary Study Objective(s):	None.
Study Population and Main Eligibility/ Exclusion Criteria:	Eligibility: Patients between ages 18-80 with confirmed diagnosis of cystinuria with a medical regimen that includes Tiopronin who are willing to complete a 24h urine collection and food diary. Female patients at childbearing age who are willing to use a contraception method. Exclusion Criteria: Patients who are unwilling or unable to provide informed consent, pregnancy, patients with renal colic or patients who are scheduled for a urological procedure.
Treatment	
Agent-	Tiopronin
Dosage, schedule, route of administration-	500mg PO daily x 7 days, then 500 mg PO BID x 7 days, then 1g PO BID x 7 days
Safety Issues-	Allergy or drug side effects
Primary Outcome Measures:	Urine cystine capacity
Secondary Outcome Measures:	Urine volume, pH, urea, sodium, creatinine, cystine concentration, and urinary cystine supersaturation
Statistical Considerations (sample size and analysis plan):	The impact of CBTD dose on CysCap will be analyzed with a mixed effects model, with subject as a repeated factor, and including dose and period effects.

Sponsors (federal, state, foundation and industry support):	National Institutes of Health (NIH), NIDDK, ORDR
--	--

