## 1.1 Overview:

The purpose of this study is to determine the minimum effective dose of the cysteine binding thiol drug (CBTD) Tiopronin on urine cystine capacity, which is a measure of cystine solubility in the urine, in patients with cystinuria.

Cystinuria is a rare genetic disease that can lead to significant morbidity in affected patients due to the recurrent nature of the disease. As a result, a significant part of treatment is focused on prevention of stone formation. Current methods of prevention include increasing fluid intake, dietary modifications, alkali therapy, and CBTDs, which help increase the solubility of cystine in the urine. At present, the dosing of Tiopronin is empiric, and the drug not titrated to a specific measured effect. We propose to follow the level of urine cystine capacity in order to help guide treatment and to use lower than usually prescribed Tiopronin doses to decrease the potential side effects while keeping the same therapeutic benefit. This will increase adherence with the medications by decreasing the burden of the large number of pills that need to be taken daily.

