## 2 Specific Aims (Hypothesis and Objectives)

Our primary objective is to compare the effect of different Tiopronin doses on urinary cystine capacity (CysCap). A positive urinary cystine capacity reflects the ability of the urine to take up more cystine and therefore decrease the risk of stone formation. In a previous study, we demonstrated that Tiopronin improves cystine capacity and that the change in cystine capacity was minimal with doses above 1g.

We propose comparing the effects of lower doses of Tiopronin on cystine capacity.

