#### **4 Study Design and Methods**

Due to the low prevalence of cystinuria in the population, the number of patients available to participate in this study precludes the ability to conduct a randomized controlled trial with satisfactory probability to achieve a projected sample size. As in our recently completed study, we plan to enroll 5-10 patients in the study and perform a crossover trial in which patients receive escalating dosages of CBTDs.

Patients will be recruited from the clinical practice of the principle investigator at routine clinic visits at the Kidney Stone Prevention Clinic at NYU Langone Health. After completing informed consent, the patient will have an initial visit that will be a screening interview. During this interview, the patient will be screened for symptoms of renal colic (which if present would exclude him/her from eligibility), as well as asked about any scheduled urologic procedures. A medication history will be taken at this time, and the subject's most recent bloodwork (including a complete blood count) and most recent urinalysis will be reviewed. The total time for this visit should be approximately 20 minutes. The remainder of the study will be performed at home.

There will be four parts to the study. Each part will be divided into a 7-day period in which patients will be taking different dosage of Tiopronin and will have a urine collection at the end of each period. Patients will stop taking their medications for one week in the first part. The dosage of Tiopronin in the following parts will be as follow: 500 mg for the second part, 1g for the third part and 2g for the third part. Unlike the previous study, there will not be a 3g dosage week.

A 24-hour urine collection will be performed on day 7 of each study period. The order in which the four parts of the study are performed will be randomized for each subject, in order to prevent an order effect. After a subject is enrolled in the study, the order in which he/she will perform the study periods will be determined by a computer program that generates a random order of the numbers 1-4. There will not be a specified wash-out period in between study periods due to the short half-life of Tiopronin. With the exception of Tiopronin, the patients will continue all of their regular medications including alkali therapy.

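### Enrolment is given as 5-10 in one place and 15 in two others, and the 85% power covers only the 0 versus 1 contrast, with no rule for concluding that a lower dose keeps the benefit

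*Combined protocol and SAP*

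**What the plan says.** **Enrolment.** Section 4 (Study Design and Methods): "we plan to enroll 5-10 patients in the study". The sample size section (6421 Sample Size): "We plan to enroll 15 participants in this protocol". The Synopsis also gives 15.

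**Basis of the sample size.** "In a previous study, we saw the highest change in CysCap between dose 0mg/d vs. dose 1mg/d". Then: "With this large effect size, we would need 9 participants", at P=0.05 and 85% power. No effect size, SD, sidedness, test or dropout rate is given. The unit in that sentence is mg/d. Section 4 lists the doses to be compared as 0 g/d, 500 mg/d, 1 g/d and 2 g/d, and Section 3 lists the earlier study's doses as 1, 2 and 3 g.

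**Aim.** The Synopsis objective is broad: "To evaluate the effect of escalating doses of cystine binding thiol drugs on the cystine capacity of the urine". Section 2 is similar. Section 1.1 is narrower: "The purpose of this study is to determine the minimum effective dose", with lower doses meant to "decrease the potential side effects while keeping the same therapeutic benefit". Section 3 repeats that aim.

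**Analysis.** The Synopsis and Section 6 assign the effect of dose on cystine capacity to a mixed model with dose and period effects. The short Statistical Considerations section after the sample size adds a Friedman test and GLS regression, without ranking the methods. No margin, equivalence test or rule for naming a minimum effective dose appears.

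**The concern.** There are two separate problems.

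First, the enrolment figures contradict each other in current text. The whole range 5-10 lies below 15, and four of its six values (5, 6, 7, 8) lie below 9. Section 5.7 allows the study to close once accrual is met, so which figure is the target matters in practice.

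Second, the only power statement concerns the largest difference seen before. Whether a lower dose keeps the benefit of a higher one turns on differences between active doses, 0.5 versus 1 g and 1 versus 2 g, which may be much smaller. The plan gives neither precision for those differences nor a rule for interpreting them. Section 8.2 expects lower prescribing if a maximal beneficial dose is found, so the wording of that conclusion has consequences.

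**Working it through.** **Inputs from the documents:** n=9, P=0.05, power 85%, contrast 0 versus 1 (sample size section); 15 (Synopsis, sample size section); 5-10 (Section 4). **Assumed:** two-sided test; paired t-test unless stated; equal SD of within-subject differences for all contrasts unless varied. The standardised results do not depend on the dose unit.

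**1. The plan's own figure.** The 9 cannot be reproduced forwards without an effect size and SD. It can be inverted. Power = P(|T| > t(0.975, n-1)), where T is noncentral t with noncentrality dz × √n and dz is the mean difference divided by the SD of differences.
- n=9, df 8, power 0.85 gives dz = 1.142.
- n=8 reaches 0.85 at dz = 1.238, so 9 is the smallest adequate n for dz from 1.142 up to 1.238.
- If the 9 came from a mixed model with error df (9-1)×3-3 = 21, dz = 1.048.

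All are large effects. The 9 is plausible but cannot be verified.

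**2. Power for 0 versus 1 across the enrolment figures (paired t).**

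| n | dz 1.142 | dz 1.238 |
|---|---|---|
| 5 | 49% | 56% |
| 6 | 61% | 68% |
| 7 | 71% | 78% |
| 8 | 79% | 85% |
| 9 | 85% | 90% |
| 10 | 89% | 94% |
| 15 | 98% | 99% |

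The 85% at n=8 is the boundary value by construction.

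**3. Is the broad objective covered?** Overall 3-df dose F-test, error df (n-1)×3-3, error variance 0.5 (so that the SD of a difference is 1), means 0, f, 1, 1 times dz with f = 0.25, 0.5 or 0.75.
- dz 1.142: 99% or more at n=15; 87-93% at n=9.
- dz 1.048: 97.5-99% at n=15; 80-87% at n=9.

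At n=15 it is covered.

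**4. Precision between adjacent doses at n=15.** Half-width in SD units = t(0.975, df)/√15; divide by dz to express it as a share of the 0 versus 1 effect.
- df 14: 2.145/3.873 = 0.554. Over 1.142 this is 48%; over 1.238 it is 45%.
- df (15-1)×3-3 = 39: 2.023/3.873 = 0.522. Over 1.142 this is 46%; over 1.048 it is 50%.

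**5. Power at n=15 for a contrast half the 0 versus 1 size.**

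| Calibration | Power |
|---|---|
| dz 1.048, df 39 | 51% |
| dz 1.142, paired | 54% |
| dz 1.142, df 39 | 58% |
| dz 1.238, paired | 61% |
| dz 1.142, paired, SD ratio 1.25 | 38% |
| dz 1.142, paired, SD ratio 0.75 | 78% |

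The SD ratio is the SD of the smaller contrast divided by that of 0 versus 1. A one-sided 0.05 test (dz 0.98-1.06) gives a similar picture: 57-62% for 0 versus 1 at n=5, and 56-62% for the half-size contrast at n=15.

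**6. Interpretation.** Failing to reject no difference does not bound the difference. Without a pre-stated loss that the interval must exclude, this holds at any n; steps 4 and 5 only show how wide the uncertainty could be at 15.

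**The case against.** Four points on the other side have force.

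- **Intended use of a non-significant result.** A reader might infer that the trial will treat non-significance between doses as proof of equal benefit. No section says so. Section 3 reports no change above 1 g in the earlier study, but Section 2 calls that change minimal and Section 3 says the higher doses had little efficacy. Those are statements about size, and nothing shows that they rested on a non-significant test. What stands is that the rule is missing.
- **Adequacy of the sample.** A reader might infer that 9 is wrong or 15 too few. The documents do not support that. The stated primary objective is an effect of dose, which 15 covers, and Section 5 calls this a pilot.
- **Meaning of minimum effective dose.** The term is undefined. It could mean the lowest dose that beats 0, which needs dose-versus-0 contrasts, including the one that was powered. The stated wish to keep the benefit supports the active-dose reading too, so both sets of contrasts belong in the report.
- **The 5-10 figure.** It follows a reference to the recently completed study and may be carried-over wording; the Synopsis and sample size section agree on 15. Actual enrolment of 5 is therefore hypothetical, but the text still contradicts itself.

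The mixed model is also already assigned to the dose effect and can yield dose differences with intervals. What is missing is its standing relative to the other two methods, since the Friedman test gives no such differences and does not adjust for period.

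**Conclusion.** The point holds in limited form and should be fixed. The enrolment contradiction, the shortfall of 5 to 8 against the required 9, the conflicting dose unit, and the lack of any margin or rule for a preserved-benefit conclusion can all be read directly from the text, with high confidence.

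The magnitudes are scenarios. They depend on back-solving the 9 under an assumed test and, except where varied, on equal SDs; the documents give no effect size, SD or 0.5 g data. On that basis, the n=15 interval for an adjacent-dose difference would extend about 45-50% of the 0 versus 1 effect either side, and power for a half-size contrast would be about 51-61% (38-78% with the SD ratio varied). None of this shows the trial to be too small for its stated primary objective.

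**What to change.** 1. Reconcile Section 4 with the Synopsis and the sample size section so that one enrolment target is stated.
2. In the sample size section, reconcile the dose unit with Section 4 and say that 85% at n=9 applies to the 0 versus 1 contrast only. Give the expected 95% CI width at n=15, using the earlier study's SD for contrasts it observed and a stated assumed SD for contrasts involving 0.5 g, which is not among the earlier doses listed in Section 3.
3. Name the mixed model with dose and period effects as the deciding analysis, with the Friedman test and GLS regression as supporting analyses. Report each dose versus 0 and the adjacent-dose differences with 95% CIs. Then either present comparisons between active doses as estimation only, or conclude that benefit is kept only if the CI excludes a pre-stated loss of capacity, and otherwise report the comparison as inconclusive.

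The cost is wording only, with no extra patients or samples. The power statement becomes less favourable, and a preserved-benefit conclusion may be out of reach: with truly equal doses and the paired-t calibrations, the n=15 interval would exclude a loss of half the 0 versus 1 effect about 54-61% of the time, and of a quarter about 18-20%. The estimation option avoids that risk but gives up a yes/no answer.

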### **Statistical Considerations**

Standard descriptive, repeated-measure ANOVA (Friedman test), and GLS regression will be applied.

## **7 Data Management**

Collection of all study data will comply with all applicable guidelines regarding patient confidentiality and data integrity.

### **7.1 Registration:**

All study data will be collected through REDCAP and will comply with all applicable guidelines regarding patient confidentiality and data integrity. REDCAP is a secure, web-based application for building and managing online databases. On-line forms will be developed that contain the requisite data fields.

Registration of participants on this protocol will employ an interactive data system in which the clinical site will attest to the participant’s eligibility as per protocol criteria and obtain

appropriate informed consent. IRB approval for the protocol must be on file at the DMCC before accrual can occur from the clinical site.

The DMCC will use a system of coded identifiers to protect participant confidentiality and safety. Each participant enrolled will be assigned a local identifier by the enrollment site. This number can be a combination of the site identifier (location code) and a serial accession number. Only the registering site will have access to the linkage between this number and the personal identifier of the subject. When the participant is registered to participate in the study, using the DMCC provided web-based registration system, the system will assign a participant ID number. Thus each participant will have two codes: the local one that can be used by the registering site to obtain personal identifiers and a second code assigned by the DMCC. For all data transfers to the DMCC both numbers will be required to uniquely identify the subject. In this fashion, it is possible to protect against data keying errors, digit transposition or other mistakes when identifying a participant for data entry since the numbers should match to properly identify the participant. In this fashion, no personal identifiers would be accessible to the DMCC.

## **8 Human Subject**

### **8.1. GCP Statement:**

This clinical trial will be conducted in accordance with the ethical principles that have their origin in the Declaration of Helsinki, and that are consistent with Good Clinical Practice and all applicable regulatory requirements.

### **8.2. Benefits:**

The potential benefits of this study are:

There are no direct benefits to participating in this study. However, if there is a maximal beneficial dose of Cystine Binding Thiol Drugs, then physicians will be able to minimize potential side effects of the drugs by prescribing lower doses overall, and patients will not be burdened with taking extra unnecessary pills. The results of the study may help guide treatment of patients with cystinuria with Tiopronin in the future.

### **8.3. Risks:**

The potential risks of this study are:

CBTDs are associated with allergy and other side effects including fever, central nervous system depression, anorexia, nausea, vomiting, loss of taste, abdominal pain, and myalgia. More serious adverse effects include nephrotic syndrome, hypersensitivity reactions, transient blood dyscrasias, aplastic anemia, neutrophilic agranulocytosis, neutropenia, thrombocytopenia, bronchiolitis obliterans, rashes, dystonia and various autoimmune responses (polymyositis, myasthenia gravis, SLE, Goodpasture's syndrome, thyroiditis). Although the side effects are considered idiosyncratic and not clearly dose related, there is a risk that a patient could develop a

new side effect at a drug dose that is higher than their usual dose. Since all patients are already taking the drugs for inclusion and demonstrated good tolerance, it is very unlikely that a patient will develop a significant new allergy.

Performing multiple 24-hour urine collections over the course of four weeks may be burdensome, but it is non-invasive and should not cause any pain or discomfort.

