#### **4.1 Inclusion Criteria:**

- Age between 18 and 80 years.
- Patients with a confirmed laboratory diagnosis of cystinuria who meet the following criteria: (1) stone analysis demonstrating cystine as a component, or (2) increased urinary cystine excretion (>250mg/24hrs in adults).
- A medical regimen that includes Tiopronin.
- Female patients who are willing to use a birth control method.
- Ability to reliably urinate in a collection vessel and measure urine volume.
- Ability to give informed consent.
- Documentation of a stable complete blood count (CBC) and urinalysis (UA) in the six month period prior to the date of enrollment.
- Enrollment in Rare Kidney Stone Consortium (RKSC) Protocol 6401 (Cystinuria Registry)

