#### **4.1 Exclusion Criteria:**

- Pregnant patients.
- Patients with renal colic
- Patients who are scheduled to undergo a surgical procedure
- Inability to give informed consent

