#### 4.4 Schedule of Events:

	Baseline (Visit 1)	Day 7	Day 14	Day 21	Day 28	Day 29-60
Demographics (sex, date of birth)	x					
Baseline stone history (diagnosis date and method of diagnosis, review of current symptoms)	x					
Medication history (Current medications including Alkali therapy, and history of CBTDs including side effects, allergic reactions)	x					
Dietary history (fluid intake, low sodium, low protein, etc)	x					
24-hour urine collection		x	x	x	x	
Pregnancy Test	X					

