## **5.3 Expected/Known Risks/Discomforts/Adverse Events Associated with Study Intervention and Procedures: Definition of Expected Adverse Events:**

The period off Tiopronin is only a week. During that period, the patients will continue their alkali therapy, if prescribed, and their usual fluid intake and dietary restrictions. Therefore the week off Tiopronin is extremely unlikely to lead to cystine stone formation. That is particularly true since dosing of Tiopronin is completely empirical and not based on cystine supersaturation values; in other words, the doses have not been titrated to a particular level to achieve a particular therapeutic effect. In the previous study, no episodes of renal colic occurred during the week off Tiopronin.

Tiopronin is associated with allergy and other side effects, most of which are considered idiosyncratic and not clearly dose-related. Patients will take 0.5-2g, which is less likely to exceed their usual doses. The duration at each dose is a week. Since all patients are taking the drugs for inclusion, it is again very unlikely that patients will experience any important allergy or toxicity of the drugs in the short time they take doses different than their usual doses.

Patients will be closely monitored during the time in the study and will have frequent contact with the investigators in order to report any AEs in the course of the study. Patients will be contacted by phone at least weekly to be asked about any potential adverse effects.

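### No eligibility criterion uses the tiopronin reaction history taken at Visit 1, so a patient with a past allergic or dose-limiting reaction can be enrolled and given the 2 g/d week

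*Combined protocol and SAP*

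**What the plan says.** **Who may enter.** The only drug-related inclusion item in Section 4.1 is "A medical regimen that includes Tiopronin", with no minimum dose, duration or tolerance condition. The only safety-related laboratory item is "Documentation of a stable complete blood count (CBC) and urinalysis (UA) in the six month period prior to the date of enrollment". The exclusion list has four entries: pregnancy, renal colic, inability to consent and "Patients who are scheduled to undergo a surgical procedure". The Synopsis gives a similar list, including "patients with renal colic or patients who are scheduled for a urological procedure". Neither list mentions a past reaction to tiopronin.

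**What is collected.** The medication history at Visit 1 (Section 4.4) covers "history of CBTDs including side effects, allergic reactions".

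**What is given.** The Synopsis and Section 4 schedule each participant for 0, 500 mg, 1 g and 2 g per day, one week each. Section 4 randomises the order for each participant.

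**How the risk is argued.** Section 8.3 says "Since all patients are already taking the drugs for inclusion and demonstrated good tolerance" and concludes that a significant new allergy is very unlikely. Section 5.3 says "Patients will take 0.5-2g, which is less likely to exceed their usual doses" and that "it is again very unlikely that patients will experience any important allergy or toxicity of the drugs" in the short time at a dose other than the usual one.

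**The concern.** The plan asks the right question at Visit 1 and then attaches no decision to the answer. Some patients will be on a low dose because a higher one caused a rash, vomiting or a laboratory abnormality. Such a patient is still taking tiopronin, so current use admits them. The protocol then assigns 2 g/d, which may be the dose that caused the trouble.

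What is at stake is avoidable harm to an identifiable person. Section 8.2 states that participants gain no direct benefit. The risks listed in Section 8.3 include hypersensitivity reactions, nephrotic syndrome and agranulocytosis. The information needed to prevent the re-exposure is already in hand before the first dose.

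The point does not extend to patients who have simply never taken 2 g/d. Section 8.3 discloses the risk of a new side effect above the usual dose, and accepting that risk is a legitimate design choice.

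**Working it through.** No figure in the plan bears on this point, so there is none to reproduce. The check is to take concrete patients through the text.

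**Three illustrative patients, each now stable on 1 g/d**
- A: past allergic rash on tiopronin.
- B: cut from 2 g/d to 1 g/d because of vomiting.
- C: cut from 2 g/d to 1 g/d because of proteinuria, since resolved.

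**Step 1. Are they eligible?** The inclusion items in Section 4.1 are age, confirmed diagnosis, a regimen containing tiopronin, contraception for women, ability to collect urine, consent, stable blood count and urinalysis, and registry enrolment. A and B can meet all of them. So can C, if the proteinuria resolved on the lower dose early enough for the results of the last six months to be stable. None of the four exclusions applies, and the Synopsis adds nothing on reactions. All three are eligible.

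**Step 2. Are they assigned 2 g/d?** Yes. Section 4 gives all four parts to each participant. No rule lets a participant skip or reduce the 2 g/d week because of past intolerance. Because the order is random, that week can come first or directly follow the week off drug.

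**Step 3. Do the two reassurances cover them?**
- Section 8.3 reasons from current use to a low chance of a *new* allergy. For A, B and C the reaction is not new, and tolerating 1 g/d is not evidence of tolerating 2 g/d.
- Section 5.3 says the study doses are unlikely to exceed usual doses. For these patients 2 g/d is twice the usual dose (2 / 1 = 2).

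**Step 4. Do the other safeguards close the gap?**

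| Safeguard | What it does | What it leaves open |
|---|---|---|
| Screening interview (Section 4) | Takes the medication history | Renal colic is the only answer said there to exclude a patient |
| Stable blood count and urinalysis (Section 4.1) | Screens for current laboratory toxicity | Does not detect a past rash or vomiting (A, B), and can be normal after recovery on a lower dose (C) |
| Weekly calls (Sections 4.3, 5.1) | Ask about symptoms | Act after enrolment and cannot reveal a silent laboratory change |
| Investigator withdrawal (Section 5.8) | Removes a participant | Discretionary and after enrolment |
| Eligibility attestation (Section 7.1) | Site confirms the protocol criteria | The criteria are silent on reactions |

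Each safeguard helps. None is a written rule that keeps A, B or C from being dosed at 2 g/d.

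**The case against.** **The tolerance evidence is favourable.** Section 3 says the higher doses in the previous study were well tolerated, and Section 4 says no adverse effects occurred at doses up to 3 g. This stands as a reason to expect few such patients. It does not show how patients with a known reaction fare, because the documents do not say whether any took part.

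**Side effects are described as idiosyncratic and not clearly dose-related** (Sections 5.3, 8.3). If so, B and C may face no more risk at 2 g/d than at 1 g/d. That is a fair challenge to any claim that recurrence is likely. It does not remove the point: a patient who has already reacted has shown a susceptibility. For allergy, the same premise argues for an exclusion at any dose rather than only at 2 g/d or below.

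**A sensible investigator would decline such a patient.** Probably so. Nothing in Section 7.1 obliges the site to enrol everyone who qualifies, and many participants will be known to the clinic. But Sections 4.2 and 8.4 also recruit from the registry by phone, mail or email. A protocol that already asks about reactions should state what a positive answer means.

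**Stronger readings that a reader might infer, and that the documents do not support**
- *That the gap raises the chance of stopping the study by some stated amount.* Section 5.7 does have a one-event rule, but the documents give no reaction or recurrence rates, so any figure would be invented. The rule names allergic manifestations and symptoms that lead to intolerance, so a silent laboratory change is not clearly covered. The severity of that rule is a separate matter.
- *That it delays detection of laboratory toxicity.* The only scheduled post-dose blood count and urinalysis come within a month of completion, but that applies to every participant. It concerns the monitoring schedule, not eligibility.
- *That it costs power.* The 9 in the sample-size section comes from the previous study's contrast of 0 with a dose printed as 1 mg/d (presumably 1 g/d). Section 5.8 keeps data obtained before a withdrawal. No loss can be derived.

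**Conclusion.** The concern holds as a gap in eligibility. As written, the criteria admit a patient with a past allergic reaction to tiopronin, or one reduced because of an adverse effect at 2 g/d or below, and assign that patient the 2 g/d week. The statement on tolerance in Section 8.3 is a rationale, not a criterion, and does not cover this patient.

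The size is modest. The frequency cannot be estimated from the documents and is probably low. The exposure is one week at a dose that Section 3 treats as ordinary clinical practice. The conclusion rests on two assumptions: that some patients remain on tiopronin at a reduced dose after a reaction, and that such a history is clinically relevant to re-exposure. Neither is quantified in the plan. The change is still worth making, because it alters who is dosed, uses data already collected and costs little.

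**What to change.** Add one line to the exclusion criteria in Section 4.1 and to the Synopsis, applied at Visit 1 before the dose order is generated:

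> History of an allergic or hypersensitivity reaction to tiopronin at any dose, or of an adverse effect (symptom or laboratory change) at 2 g/d or below that led to a sustained dose reduction or discontinuation, unless the patient has since taken 2 g/d or more without recurrence.

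Have the Visit 1 medication history record the current tiopronin dose and, for each past reaction, the dose at the time, the action taken and whether 2 g/d or more was later taken without recurrence. Reword Section 8.3 so that its statement on tolerance rests on this criterion rather than on current use.

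A patient with mild effects who stayed on 2 g/d remains eligible, as does one with a brief interruption who resumed the same dose, unless the reaction was allergic and recurred or 2 g/d has not since been taken.

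**Cost.** One line in two places and a few fields on a history already taken. A few otherwise eligible patients are lost, including some who cannot take higher doses and whom a study of the minimum effective dose would hope to help. The pool is small. The sample-size section plans 15 against a stated need of 9, a margin of 15 − 9 = 6. If enrolment reached only 10, the upper figure in Section 4, the margin would be 10 − 9 = 1. The later-tolerance exception limits the loss.
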